### 2.6 Study duration

Provisional total duration of the study: 21 months (nine-months inclusion period + 1-year follow-up period).

All included patients will be followed up for a period of one-year nominal. The participating physicians will be given a period of nine months to enroll patients. The study will be completed as soon as the last patient included has undergone an evaluation of one year after inclusion in the study.

An interim statistical analysis will be performed after the last patient has undergone its 6 months follow-up. Data obtained from all included patients, up to the 6-months follow-up, will be used to write this interim report.

### 3 SELECTION OF PATIENTS

#### 3.1 Patient selection method

Once the study has been initiated, the investigator will recruit the 60 to 120 patients (120 eyes) in an expected period of 6 months. The inclusion period will end at the inclusion of the last patient.

During this period, the investigator will invite all patients for whom the decision has been made to implant a Lucidis lens to take part in the study, so as to include all patients fulfilling the study inclusion criteria in a consecutive manner.

Prior to inclusion and before carrying out any study-related procedures, the investigator will first inform each patient of the study objectives, the conditions for their participation in the study, and the need to allow the study monitor to have direct access to their medical records. Patients will be given an information leaflet and informed consent form, which they are required to personally date and sign.

Before implanting the Lucidis lenses with any of the following conditions, pre-operative evaluation is performed by the surgeon to consider the potential benefit/risk ratio. In case of contraindications, ie the patient already has pathologies or physiological conditions, which may be aggravated by the lens, or in cases where the lens may interfere with the possibility of examining or treating diseases, the lens will not be implanted and the patient will not be included in the study.

Additionally to exclusion criteria, the risk/benefit ratio is individually assessed for each patient with regards to safety and patient vision performance expectations. Diagnostic, anamnesis, eye biometry combined with way of life and patient expectations are considered prior the selection by the surgeon or proposal to the patient to implant a Lucidis IOL. Lucidis is an EDOF (Extended Depth Of Focus) intraocular lens that provides near and intermediate vision in addition to distance vision. Should a patient's medical status or visual expectations determined as not in adequacy with the device, alternative available devices - such as monofocal or multifocal intraocular lenses would be implanted instead. The choice of the intraocular lens based on the state of the art is an essential parameter evaluated in depth by the physician (through diagnosis, anamnesis, comorbidities, biometry, lenses optical performances, dysphotopsia, patient way of life and expectations, etc.).

#### 3.2 Selection Criteria

- adult patients (≥18 years)
- having agreed to take part in the study and complete post-operative follow-up requirements (by having signed the information leaflet-informed consent form);
- significant reduction in visual acuity and/or visual comfort from cataract;

- for whom the physician made the decision to implant a Lucidis based on medical considerations.

### **3.3 Non-inclusion criteria**

The following will not be included in the study:

- patient included in an interventional therapeutic trial at the time of inclusion;
- patient presenting contraindications for the implantation of an intraocular lens;
- patient presenting an ophthalmic disorder liable to interfere with the study endpoints;
- patient presenting with an astigmatism  $\geq 1.0$  D;
- patient refusing or unable to comply with the follow-up procedures in the study (patient unable to be reached by telephone, liable to be lost to follow-up, etc.);
- History of previous intraocular surgery in the study eye in the previous 6 months;
- patient is pregnant, breast-feeding or unable to make the decision to participate in a clinical investigation (e.g. mentally ill or handicapped person)

## **4 PRACTICAL IMPLEMENTATION OF THE STUDY**

This study does not affect the physician-patient relationship, or usual patient management. The physicians remain free in their prescribing and follow-up practices; no specific procedures or examinations are requested. The study remains within the normal treatment context.

### **4.1 Study initiation**

Before the first patient is included in the study, the study protocol, case report forms and completion guidelines, the procedure for obtaining informed consent, together with the procedure for reporting adverse events will be explained to the investigator during the initiation visit.

## 4.2 Treatment

The surgical procedures for implanting the lens are left to the discretion of the investigator according to his/her practices. All treatments administered in the context of implantation should also be reported in the "concomitant medication" section of the CRF.

## 4.3 List of data collected

The physician will fill in a paper case report form (p-CRF) for each patient's eye, comprising:

### 4.3.1 Data collected at inclusion:

- Date of inclusion;
- Verification of inclusion and exclusion criteria;
- Declaration by the physician that the patient has signed the information leaflet and informed consent form;
- Demographic data (age at inclusion, gender);
- Candidate eye for operation (uni- or bilateral in nature)

### 4.3.2 Data collected at baseline visit (pre-operative):

- Cataract history: age of onset, type of cataract;
- Pre-operative ophthalmological examination: standard slit-lamp examination, visual acuity in photopic and mesopic conditions (uncorrected visual acuity for near, intermediate (80cm), and far vision & best corrected visual acuity for far vision), contrast sensitivity and aberrometry.

### 4.3.3 Data collected on the day of surgery:

- Operated eye
- Lens information
- General surgical procedure information (Constant value including formula biometry, type of anaesthesia, incision site). The choice of the formula is left to the discretion of the investigator. However, it shall be the same for all patients.
- Adverse event during surgery

### 4.3.4 Data collected after surgery at day 1:

- Postoperative ophthalmological examination: standard slit-lamp examination, visual acuity in photopic and mesopic conditions (uncorrected visual acuity for near, intermediate (80cm), and far vision &

best corrected visual acuity for far vision), contrast sensitivity, aberrometry and defocus (defocus will be measured for the first 40 patients as a minimum) at the discretion of the investigator.

- Adverse events spontaneously reported by the patient;
- Specific interview concerning visual acuity, frequency of glare and halo, distorted vision.
- Possible postoperative complications
- Change in medication intake

#### 4.3.5 Data collected after surgery (at week 1, month 1, month 6, year 1):

- Postoperative ophthalmological examination: standard slit-lamp examination, visual acuity in photopic and mesopic conditions (uncorrected visual acuity for near, intermediate (80cm), and far vision & best corrected visual acuity for far vision), contrast sensitivity, aberrometry and defocus (defocus will be measured for the first 40 patients as a minimum).
- Adverse events spontaneously reported by the patient;
- Specific interview concerning visual acuity, frequency of glare and halo, distorted vision.
- Possible postoperative complications
- Change in medication intake

### 4.4 Evaluation schedule

The initial evaluation during the inclusion and baseline visit is done from 1 to 14 days before the date of surgery.

The evaluation schedule will then correspond as follows, for each eye:

- Day of surgery
- Day 1 (0 to 3 days after surgery)
- Week 1 (7 to 10 days after surgery)
- Month 1 (30 to 45 days after surgery)
- Month 6 (180 to 195 days after surgery)
- Year 1 (360 to 390 days after surgery).

If it is not possible to perform a visit, it must be documented and justified on the p-CRF. See also chapter 4.5 for lost patients follow-up.

Evaluation of efficacy and long-term safety for Lucidis  
Instant Focus© - PMCF Study protocol

Version 9 - Page 13/25

SWISS ADVANCED VISION

INTRAOCULAR LENS

In case of bilateral surgery, the Month 6 and Year 1 follow-up visits of each eye can be combined together into 1 visit, if within the timeframe. After the second eye's surgery, visual acuities are additionally measured as bilateral.

# Evaluation of efficacy and long-term safety for Lucidis Instant Focus© - PMCF Study protocol

Version 9 - Page 14/25

SWISS ADVANCED VISION

INTRAOCULAR LENS

Collected data	Screening (study inclusion)	Baseline visit (D - 14-1)	Surgical procedure (D)	Follow-up Day 1 (D1-2)	Follow-up Week 1 (D7-10) Follow-up Month 1 (D30-45) Follow-up Month 6 (D180-195)  Follow-up Year 1 (D360-390) 
Informed consent	X				
Demographics	X				
Inclusion / exclusion criteria	X				
Candidate eye(s) for operation	X				
Slit lamp examination		X		X 	X
Cataract history		X			
Contrast sensitivity Photopic (85–100 lx) and Mesopic (3 lx)		X		X 	X
Uncorrected Visual Acuity – Far Photopic (85–100 lx) and Mesopic (3 lx)		X		X 	X
Uncorrected Visual Acuity – Intermediate Photopic (85–100 lx) and Mesopic (3 lx)		X		X 	X
Uncorrected Visual Acuity – Near Photopic (85–100 lx) and Mesopic (3 lx)		X		X 	X
Best Corrected Visual Acuity - Far		X		X 	X
Defocus curve* Photopic (85–100 lx) and Mesopic (3 lx)		X		X 	X
Abberometry		X		X 	X
Operated eye			X		
Lens information			X		
General surgical procedure information			X		
Adverse event during surgery			X		
Adverse event spontaneously reported by patient				X	X
Specific interview: visual acuity, frequency of glare and halo, distorted vision				X	X
Change in medication intake				X	X

\*only for the first 40 patients. In case of patient withdrawal, data will be collected on a new patient to obtain data on a minimum 40 patients, whenever possible.

X: at the discretion of the investigator

: Additional follow up visits compared to standard procedure

## 4.5 Patients lost to follow-up

A patient will be considered lost to follow-up if s/he does not attend a scheduled visit and if the investigating physician is unable to obtain any news on the patient in the next two months after making every attempt to contact the patient.

During contact, the investigating physician will ask the patient about the reasons for not attending the scheduled visit (moved house, personal decision for example) and his/her decision regarding participation in the study and continued management.

#### **4.6 End of study - withdrawal from the study**

The patients will be considered to have completed the study after they have undergone a final evaluation 1 year after the inclusion visit.

The following may be considered to have withdrawn from the study:

- Patients who have requested to do so (verbal or written) via the investigator;
- patients lost to follow-up by the center, unable to be reached;
- Included patients presenting an exclusion criterion during the study (for example, inclusion in an interventional therapeutic trial).

In case of withdrawal of informed consent, non-compliance, disease progression, safety, etc. the study procedures might be stopped but the routine follow-up should be performed due to safety concerns. Data previously obtained will be retained and analyzed.

#### **4.7 Monitoring**

The sponsor, or an individual independent from the study and appointed by the sponsor, will perform monitoring visits, at study initiation, after one of the evaluation schedule and at study completion, as a minimum, to oversee progress in accordance with this protocol.

### **5 ASSESSMENT METHODS**

At each visit the patient will be seen by both an ophthalmologist and an optometrist. The qualified optometrist will carry out all examinations regarding visual acuity, contrast sensitivity and aberrometry. The investigating ophthalmologist will collect data through slit-lamp examination, and through interviewing the patient about any unusual sensations or adverse events based on the patient's impressions, observations and response to the question: "How are you feeling?" or "How have you felt since the last visit?". Adverse events will be recorded. An anomaly persisting at the end of the study will be monitored by the investigator until they resolve or at least stabilize.

## 6 ADVERSE EVENTS

### 6.1 Definitions

#### 6.1.1 Definition and classification of adverse events:

An adverse event is a harmful occurrence in a person taking part in a biomedical study, whether or not this event is related to the study or study product. An adverse event can therefore be any unfavorable and unintended sign (including an abnormal laboratory finding), symptom, or disease temporally associated with the use of the product, whether or not this is considered to be related to the use of the product (International Conference on Harmonisation, ICH).

A serious adverse event (SAE) is an event which:

- results in death;
- is life-threatening to the person taking part in the study;
- requires inpatient hospitalization ( $\geq 24$  hrs) or prolongation of existing hospitalization;
- results in persistent or significant disability/incapacity;
- or is a congenital anomaly/birth defect.

A life-threatening risk is an event which places the subject at immediate risk of death at the time of the event; this does not refer to an event which hypothetically may have caused death if it were more severe.

Any medically significant event which, according to the assessment based on the investigator's medical and scientific knowledge, while not immediately life-threatening, may result in the death of the patient, require inpatient hospitalization, endanger the patient, require medical or surgical intervention to prevent progression to one of the above-mentioned situations, should be perceived as serious.

Temporary transfer to a hospital outpatient clinic, an admission's department or day hospital ( $< 24$  hrs) or inclusion in a home hospitalization system not leading to administrative hospital stay measures, is not perceived as hospitalization.

Any hospitalization occurring during a study should be reported to the sponsor by the investigator (as soon as it is brought to his/her attention).

Therefore, the following types of hospitalization are not subject to declaration: required surgical intervention planned prior to inclusion in the study, for investigations stipulated in the protocol, as a simple precautionary measure for monitoring after overdose in a patient not presenting any clinical, paraclinical or laboratory anomalies, or related to specific social circumstances affecting the patient. Any pregnancies during the study will be considered an SAE.

Unexpected adverse event: any event the nature or severity of which is not in the product instruction for use.

### **6.1.2 Causal relationship of adverse event**

The causal relationship of the adverse event should be based on the following classification:

- device related: potential imputability with the device
- surgery related: potential imputability with the surgical procedure
- other.

### **6.1.3 Severity of the adverse event**

The severity of the adverse event should be based on the following classification:

- mild: generally transient, does not affect the patient's normal daily activities;
- moderate: interferes with the patient's daily activities and/or sleep;
- severe: prevents the patient's daily activities and/or sleep.

## **6.2 Procedures**

### **6.2.1 Serious adverse events and pregnancy**

Serious events are not expected in the context of this study, which is the treatment of cataract.

However, in case of serious adverse events and/or pregnancies occurring during the study, must be reported to the study sponsor by fax or mail within 24 hours of the event being notified. This report must be signed and dated by the investigator and faxed or mailed to:

[name]  
[contact]  
Mail: [name] [[contact]](mailto:[contact])

and copy to:

[name]  
Mail: [contact]

Serious adverse events which have not resolved at the end of the study should be monitored by the investigator until they are resolved (or become consolidated) or until

there is evidence that there is no relationship between the event and the study conditions or until it is firmly believed that no additional information can be obtained.

### 6.2.2 Other adverse events

Non-serious adverse events (including exacerbation of existing disorders) should be reported on the p-CRF regardless of their causal relationship, from the signing of the information leaflet and informed consent form until the end of the last study procedure.

Investigators should give their own opinion on the relation between the event and the lens implant, describe all the measures taken as a result of the event as well as the event outcome in the p-CRF.

The sponsor is responsible for the appropriate reporting of adverse events to the authorities and the Ethics Committee that approved the protocol.

## 7 DATA COLLECTION AND ANALYSIS

### 7.1 Data collection

The investigator will receive a case report form (p-CRF) paper format for each patient for recording the evaluation results. Collected data on p-CRF will be used as source data. In case of bilateral surgery, one case report form will be completed for each eye which include bilateral visual acuity

Each patient will be assigned an identification number. The sponsor will review case report forms and collected data will be entered in Excel file at specific time (for example after monitoring visits) by an independent individual appointed by the sponsor. The entered data will be checked by another person. Then the completed cells on the Excel spreadsheet will be blocked and the document printed. The printed record must be dated and signed. The printed record will be added to the study input documentation. This file will be maintained by the sponsor who will ensure that it is valid and secure.

### 7.2 Statistical analysis

The analysis will be comparative and shall concern all patients having agreed to take part in the study. Statistical data will be evaluated for each eye, additionnaly in case of bilateral surgery visual acuity for both eyes will be analysed for each eye and together. The quantitative variables will be described in terms of sample size, mean, standard deviation, median, range and missing data. The qualitative variables will be described in terms of sample size, percentage and missing data. Two-sided 95% confidence intervals will be provided if the endpoint is considered relevant. Wilcoxon and Student significance tests will be used.

An interim statistical analysis will be performed from the 6 months data of all included patients. A final statistical analysis will be performed after the last 1-year follow-up visit of the last patient. Data will be compared to the state of the art data regarding similar lenses available on the market.

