### 2.2 Study design

This is a monocentric, longitudinal, prospective, cohort study for a population of 120 eyes on 60 to 120 patients (depending on mono or bi-lateral surgery conditions) with a cataract, receiving an Lucidis lens implant. After the cataract procedure, data collection will take place during appointments planned by the physician (after one day, one week, one month, six months and one year).

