### **7.3 Required sample size**

The total number of eyes to be included in the study is **120**. Indeed, based on the statistical calculations and standards described in ISO 11979-7:2018 regarding clinical investigations for ophthalmic implants, intraocular lenses, it is considered that 100 eyes would be sufficient to detect the appearance of any post-operative complications, at a statistically satisfactory rate of probability, and to discriminate the visual acuity results.

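### Section 7.2 has no method for correlation between a patient's two eyes, so pooled-eye tests and 95% intervals would overstate precision

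*Combined protocol and SAP*

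**What the plan says.** Section 2.2 plans "120 eyes on 60 to 120 patients (depending on mono or bi-lateral surgery conditions"), so between 0 and 60 patients may contribute two eyes. Section 7.3 also counts the sample in eyes ("The total number of eyes to be included in the study is" 120) and calls 100 eyes sufficient.

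Section 7.2 states that data are "evaluated for each eye, additionnaly in case of bilateral surgery visual acuity for both eyes will be analysed for each eye and together". For inference it says that "Wilcoxon and Student significance tests will be used" and that "Two-sided 95% confidence intervals will be provided if the endpoint is considered relevant". It adds that "Data will be compared to the state of the art data regarding similar lenses available on the market", without naming a test for that comparison.

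Section 4.4 says that after the second operation "visual acuities are additionally measured as bilateral". Section 7.1 provides one case report form per eye, each of which carries the bilateral acuity.

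No section mentions fellow-eye correlation, a clustered or mixed-model analysis, or a rule selecting one eye per patient.

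**The concern.** The ordinary Student and Wilcoxon tests, and the usual interval for a mean, assume independent observations. Two eyes of one patient share that patient. They may also share a visit: "In case of bilateral surgery, the Month 6 and Year 1 follow-up visits of each eye can be combined".

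The one clause on bilateral patients does not deal with this. Read with section 4.4, the word *together* most plausibly means binocular acuity, which is a different endpoint with one value per patient. It leaves the per-eye analyses uncorrected and does not cover contrast sensitivity at all.

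The phrase *for each eye* is ambiguous. It may mean right and left eyes analysed separately, where the problem does not arise, or all eyes pooled. Section 7.3 fits pooling better: right and left analyses divide 120 eyes between them, so they cannot both reach the 100 eyes called sufficient, and with 60 bilateral patients each has 60.

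At stake are the intervals and p-values for mean visual acuity (the primary objectives in section 1.2), contrast sensitivity and change from baseline. There is also a smaller gap: because binocular acuity sits on both eye forms, 7.2 should say that it enters the analysis once per patient.

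**Working it through.** **The plan's own figure.** The 120 eyes (100 sufficient) in section 7.3 cannot be reproduced. The section gives no event rate, standard deviation, effect size, power, dropout or inter-eye correlation.

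**Inputs**
- Eyes: n = 120 (sections 2.2 and 7.3).
- Bilateral patients: b = 0 to 60 (from 60 to 120 patients, section 2.2). Cases worked: b = 60, and b = 30 with 60 unilateral patients.
- Interval level: two-sided 95% (section 7.2). The plan states no test level; 5% is assumed to match.
- Correlation ρ between fellow eyes in the analysed level or change score: not in the documents. Assumed 0.1, 0.3, 0.5 and 0.8. Low values are included because section 3.3 excludes interfering eye disorders, which may lower it.
- Test form: one-sample or paired (assumed; 7.2 does not say).

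**Formulas.** The variance of the pooled mean is (σ²/n)(1 + 2bρ/n), so:
- design effect DEFF = 1 + 2bρ/120
- effective n = 120/DEFF
- correct interval width = √DEFF × nominal width
- actual error = 2[1 − Φ(1.96/√DEFF)]; coverage = 1 − error

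**Worked example, b = 60, ρ = 0.5.** DEFF = 1 + 120 × 0.5/120 = 1.50. Effective n = 120/1.50 = 80. Width ratio = √1.50 = 1.225. Error = 2[1 − Φ(1.96/1.225)] = 10.95%.

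| Case | ρ | DEFF | Effective n | Width ratio | Actual error | Coverage |
|---|---|---|---|---|---|---|
| 60 bilateral | 0.1 | 1.10 | 109.1 | 1.049 | 6.17% | 93.8% |
| 60 bilateral | 0.3 | 1.30 | 92.3 | 1.140 | 8.56% | 91.4% |
| 60 bilateral | 0.5 | 1.50 | 80.0 | 1.225 | 10.95% | 89.0% |
| 60 bilateral | 0.8 | 1.80 | 66.7 | 1.342 | 14.41% | 85.6% |
| 30 bilateral + 60 unilateral | 0.1 | 1.05 | 114.3 | 1.025 | 5.58% | 94.4% |
| 30 bilateral + 60 unilateral | 0.3 | 1.15 | 104.3 | 1.072 | 6.76% | 93.2% |
| 30 bilateral + 60 unilateral | 0.5 | 1.25 | 96.0 | 1.118 | 7.96% | 92.0% |
| 30 bilateral + 60 unilateral | 0.8 | 1.40 | 85.7 | 1.183 | 9.76% | 90.2% |

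With 120 unilateral patients, or ρ = 0, DEFF = 1 and the error is 5.0%.

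**Simulation check** (ρ = 0.1 / 0.3 / 0.5 / 0.8)
- 60 bilateral: t-test 6.11 / 8.57 / 10.92 / 14.63%; signed-rank test 5.84 / 8.30 / 10.93 / 14.45%.
- 30 + 60: t-test 5.61 / 6.84 / 7.99 / 9.70%; signed-rank test 5.69 / 6.80 / 7.77 / 9.65%.
- ρ = 0: t-test 4.95% and 4.98%.

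There were 100,000 runs for the t-test and 40,000 for the signed-rank test. Both agree with the formula.

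**State-of-the-art comparison.** If this were a two-sample test against an independent, unclustered group of equal size and variance (an assumption; the plan names no test), replace DEFF by (1 + DEFF)/2. The error is then 5.6 / 6.8 / 8.0 / 9.8% with 60 bilateral patients and 5.3 / 5.9 / 6.5 / 7.4% with 30 + 60.

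**Check of the remedy.** Across both cases and all four ρ values, simulated error was 4.91% to 5.06% for a t-test on patient means, 4.91% to 5.15% with cluster-robust standard errors, and 4.65% to 5.24% for a signed-rank test on patient means.

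**The case against.** The strongest reply is that the defect is conditional. It needs pooled eyes, bilateral patients and positive correlation, and the text fixes none of these. That is right, and the conclusion is stated with those conditions. What the text does establish is that the analysis unit is unclear and that no method for correlation is given.

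A second reply is that the harm is limited. This is a single-arm, largely descriptive cohort with no stated hypothesis, test level or success criterion. For change from baseline, the patients were chosen for marked visual loss, so a null of no change is hardly in doubt. This also stands. It makes interval width the figure to look at, ahead of test error, and it keeps the point below anything that would change a decision. It does not remove it: the results are reported at interim and final analysis and set against other lenses, where interval width matters.

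Third, the remedies are not interchangeable. With 30 bilateral and 60 unilateral patients, bilateral patients carry 60/120 = 1/2 of the eye-level mean but 30/90 = 1/3 of the patient-level mean. If the two groups differ by d, the estimate moves by d/2 − d/3 = d/6. GEE with exchangeable correlation also reweights. This is valid and should guide the choice of method. Cluster-robust standard errors around the ordinary eye mean leave the estimate unchanged.

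Finally, nothing says that binocular acuity would be counted twice. True; the request is only to state that it is not.

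**Conclusion.** The concern holds, and 7.2 should be amended. If it is followed with eyes pooled, its intervals are too narrow whenever there are bilateral patients and positive fellow-eye correlation. Over the assumed correlations of 0.1 to 0.8, the correct intervals are 1.05 to 1.34 times as wide when all patients are bilateral, and 1.02 to 1.18 times as wide in the mixed case.

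Against the 100 eyes of section 7.3, effective n falls below 100 once DEFF exceeds 1.2: ρ above 0.2 with 60 bilateral patients, or above 0.4 with 30. This is only a benchmark, because 7.3 does not say whether its 100 eyes are independent.

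Point estimates are unaffected, no pass/fail decision is at risk, and no figure is claimed for complication rates. The bilateral share, the correlation (which may differ between postoperative level and change score) and the form of test are assumptions.

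**What to change.** In section 7.2:
- State whether eyes are pooled or right and left eyes are analysed separately, and explain what *for each eye and together* means.
- For pooled continuous outcomes, treat the patient as the cluster. Cluster-robust standard errors around the eye-level mean keep the estimate as it is. GEE or a t-test on patient means is also valid, but say which mean is being estimated, because the weighting differs when bilateral and unilateral patients are mixed.
- Replace the ordinary Wilcoxon test with a signed-rank test on patient means or a clustered signed-rank test.
- Analyse binocular acuity once per patient.
- Report the number of patients beside the number of eyes.

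The cost is a few sentences and no new data. Each patient has an identification number (section 7.1) that appears on the case report forms (section 8.5), so the two eye forms can be linked. The price is wider intervals, by 34% at most over the range examined (all patients bilateral, ρ = 0.8).

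### Month 6 and Year 1 acuity will be averaged over whichever eyes attend, and the complication percentage has no stated denominator or allowance for follow-up time, so selective drop-out could bias both

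*Combined protocol and SAP*

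**What the plan says.** Section 7.2 is the whole analysis plan. For acuity and contrast: "The quantitative variables will be described in terms of sample size, mean, standard deviation, median, range and missing data". For complications and other categorical items: "The qualitative variables will be described in terms of sample size, percentage and missing data". For testing: "Wilcoxon and Student significance tests will be used". The analysis "shall concern all patients having agreed to take part in the study". The section does not say whether the tests are paired. It names no longitudinal model, no rule for a missed visit, no missing-data sensitivity analysis, no time-to-event method and no denominator for a complication percentage.

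Footnote 2 of the section 4.4 table labels Month 6 and Year 1 "Additional follow up visits compared to standard procedure", and section 8.1 agrees. Section 4.4 requires a missed visit to be documented and justified. Section 4.6 keeps and analyses data obtained before withdrawal. It also lets patients who meet an exclusion criterion during the study be considered withdrawn, and lets study procedures stop for reasons that include disease progression and safety, with routine follow-up continuing. The exclusion criteria in section 3.3 include an eye disorder that could interfere with the endpoints.

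Section 7.3: "The total number of eyes to be included in the study is 120", while "100 eyes would be sufficient". No drop-out rate appears anywhere.

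**The concern.** A missing count reports loss but does not adjust for it. Naming all consenting patients as the analysis population supplies no value for an eye absent at Year 1, so the visit mean rests on the eyes present. The late visits are the ones patients have least routine reason to attend. Sections 4.6 and 3.3, read together, also give an eye that deteriorates a route out of the study before Year 1. If loss follows that pattern, the eyes averaged at Year 1 are a better-seeing subset of those averaged at Month 1. Acuity could then seem stable or improving when nothing had changed, with a confidence interval centred in the wrong place.

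For complications, an eye last seen early contributes less than a year of observation. The reported percentage then depends on whether the denominator is all operated eyes or Year 1 attenders. That choice should be fixed before the data are seen, because long-term safety is a stated objective and section 7.2 compares the results with published data on similar lenses.

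**Working it through.** **1. The plan's own figures.** The 120 and 100 eyes in section 7.3 cannot be re-derived, because no rate, effect, SD, alpha, power or drop-out is given. If the difference were a drop-out reserve, 100/(1 − d) = 120 gives d = 20/120 = 16.7%; 100 × 1.20 = 120 fits equally well. Neither is stated. I use d = 16.7% as an assumption.

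**2. Acuity: bias.** Attenders' mean minus true mean = −d × δ, where δ is the drop-outs' mean logMAR minus the attenders' (positive = drop-outs see worse).
- d = 16.7%: δ = 0.20 gives −0.033; δ = 0.10 gives −0.017; δ = 0 gives 0; δ = −0.10 gives +0.017.
- δ = 0.10: d = 5% gives −0.005; d = 25% gives −0.025.

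**3. Acuity: coverage.** Further assumptions: 120 independent eyes, SD 0.15 logMAR, no true change, Month 1 and Year 1 bivariate normal, logistic missingness depending on Month 1 acuity and set to 20 of 120 missing; 6,000 simulated cohorts per setting.

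| Correlation | Odds ratio per SD of worse acuity | Year 1 mean too good by (logMAR) | Coverage of 95% CI |
|---|---|---|---|
| 0.5 | 1.5 | 0.005 | 94% |
| 0.7 | 2 | 0.011 | 88% |
| 0.7 | 3 | 0.016 to 0.017 | 80% |
| 0.9 | 3 | 0.021 | 70% |

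Check by hand: SE = 0.15/√100 = 0.015. Bias 0.011 is 0.73 SE, so coverage = Φ(1.96 − 0.73) − Φ(−1.96 − 0.73) ≈ 0.89. Bias 0.021 is 1.4 SE, giving ≈ 0.71. Both agree with the table to within a point. By step 2, a bias of 0.011 corresponds to δ = 0.011/0.167 ≈ 0.066.

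**4. Complications over all operated eyes.** Assume a true one-year risk of 5%, constant hazard and 16.7% of eyes lost. With λ = −ln(0.95) = 0.0513:
- All losses at day 45: risk accrued by then = 1 − exp(−0.0513 × 45/365) = 0.0063. Reported risk = 0.833 × 0.05 + 0.167 × 0.0063 = 0.0427.
- Losses uniform over the year: mean accrued risk = 1 − 0.05/0.0513 = 0.0252. Reported risk = 0.833 × 0.05 + 0.167 × 0.0252 = 0.0459.

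**5. Effect of the denominator.** Assume a true risk of 5%, half the events before drop-out (0.025 early, 0.025 late) and d = 16.7%. Let RR be the late risk in drop-outs relative to eyes that stay, and q = 0.025/(0.833 + 0.167 × RR). Then all eyes = 0.025 + 0.833q; all events over Year 1 attenders = that/0.833; Kaplan-Meier = 0.025 + q.

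| RR | q | Over all eyes | Over Year 1 attenders | Kaplan-Meier |
|---|---|---|---|---|
| 0.5 | 0.0273 | 4.8% | 5.7% | 5.2% |
| 1 | 0.0250 | 4.6% | 5.5% | 5.0% |
| 2 | 0.0214 | 4.3% | 5.1% | 4.6% |

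**6. Does modelling repair it?** Regressing Year 1 on Month 1 (the maximum-likelihood estimate) removes the bias in step 3, but that is built in: missingness was made to depend on Month 1 alone. If all 120 eyes come from 60 bilateral patients, which section 2.2 allows, and fellow eyes correlate 0.5 to 0.7 (assumed), the same estimate with eye-level standard errors covers only about 87% to 89%. The model therefore needs a patient term.

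**The case against.** A reader might infer that drop-out will make Year 1 acuity too good and complication risk too low. The documents support neither as a certainty. They give no drop-out rate and no direction. Satisfied patients may also skip non-routine visits; if drop-outs see as well or better, the acuity bias is zero or reverses. For complications, understatement requires all operated eyes as the denominator, which section 7.2 does not state. Over Year 1 attenders the same data overstate the risk (step 5).

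A reader might also take 120 against 100 eyes as a planned loss of 20. Section 7.3 does not mention drop-out.

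The effects are modest. The central bias of 0.011 logMAR is below one standard error (0.015). The gap between 5% and 4.27% is 0.0073 × 120 ≈ 0.9 of an eye. The plan sets no acceptance limit that such a shift could cross.

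The protocol also works against loss. Section 3.3 excludes patients likely to be lost, section 4.4 lets the late visits of two eyes be combined, section 4.5 requires attempts at contact, section 4.6 continues routine follow-up, and section 8.4 reimburses travel. The planned tests may be paired, which would compare like with like.

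All of this limits the size and certainty of the bias. What remains is that the methods listed cannot adjust for an eye missing at Year 1, and that nothing fixes the complication denominator or accounts for follow-up time. Pairing, if intended, would protect a within-eye change but would still describe attenders only.

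**Conclusion.** The concern holds as a gap in method that leaves the late results open to selective loss, not as a demonstrated bias. Under the assumptions in step 3, Year 1 acuity would look better by about 0.005 to 0.021 logMAR, with 94% to 70% coverage, and only if worse-seeing patients leave more often. Sections 4.6 and 3.3 make that direction plausible but do not establish it. A true 5% complication risk would read about 4.3% to 4.6% over all operated eyes, and about 5.1% to 5.7% over Year 1 attenders. The 16.7% loss, the SD, the correlations, the odds ratios and the 5% risk are all assumed.

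Nor does a model or Kaplan-Meier guarantee an unbiased answer. Both correct for loss explained by what has been observed. If drop-outs have twice the late risk, Kaplan-Meier still gives 4.6% against 5%. The change is worth making because it uses Week 1 and Month 1 data already scheduled and is better than the visit summaries alone.

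**What to change.** Amend section 7.2 to:

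1. Estimate Month 6 and Year 1 acuity and contrast sensitivity, and their change from Month 1, from a likelihood-based repeated-measures model using all post-operative visits of every implanted eye, with eyes clustered within patient.
2. Show same-eye (paired) changes beside the visit means, with the number of eyes in each.
3. Report complications as one-year cumulative incidence among all implanted eyes, censored at last contact, with patient-clustered confidence intervals.
4. Add a simple sensitivity analysis for loss that depends on unobserved outcomes. For example, shift the missing Year 1 acuities by 0.10 and 0.20 logMAR in the worse direction, and vary the late complication risk in lost eyes from half to twice that of retained eyes.

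The cost is section 7.2 wording and a little more programming. No extra visits or measurements are needed. The Year 1 figures may look slightly less favourable, and clustered intervals may be wider than eye-level ones.
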